5.7 Outcomes Research Assessments

5.7.1 Patient-reported Outcomes (PRO) Assessments

To assess the impact of treatment on patient-reported outcomes, two questionnaires will be used:

- 1) M.D. Anderson Symptom Inventory Multiple Myeloma module MDASI-MM (Appendix 4), which measures symptoms.
- 2) EuroQol Group's EQ-5D (Appendix 5), which measures utilities, and is a preference-based measure of health status.

Questionnaires will be administered to all subjects per the schedule in [Table 5.1-1](#), [Table 5.1-2](#) and [Table 5.1-3](#).

All questionnaires will be administered at (1) baseline (prior to randomization); (2) on Day 1 of each 4 week treatment cycle; (3) at the end of treatment or study withdrawal; (4) at each survival follow-up at the post treatment phase of the study via telephone. Traditional telephone communication between research staff and patient, or automated interactive voice response (IVR) system may reduce the burden of missing data in monitoring patient reported outcomes while they are away from the clinical sites. EQ-5D has been validated in paper, telephone interview, as well as IVR formats. Telephone interview scripts in local languages, detailed training and instructions will be provided to field staff administering the questionnaire.

Subjects should fill out the questionnaire prior to any study-related procedures, treatment or clinical assessment in order to prevent these variables from influencing PRO results. PRO instruments are provided as part of the CRF. Questionnaires will be provided in the subject's preferred language.

M. D. Anderson Symptom Inventory (MDASI) is reliable, valid instrument that was designed for ease of administration and that asks patients to rate 13 symptoms (“core” items) and 6 symptom-related interference items that are common across cancer types and treatments. The multiple myeloma module of the MDASI (MDASI-MM) is a site-specific module that augments the 19 core MDASI symptom and interference items with additional items identified as unique to multiple myeloma. Along with the core MDASI’s 13 symptom items and 6 interference items, the MDASI-MM also assesses 7 multiple myeloma-specific symptom items: bone aches, muscle weakness, sore mouth/throat, rash, difficulty concentrating, constipation, and diarrhea.

EuroQol Group’s EQ-5D:

Because oncology therapies may positively or negatively affect a patient’s quality of life, a common methodological approach is used to quantify this effect by “quality adjusting” survival in comparative treatment arms. The result, quality adjusted life years (QALYs), is a measure of both the length and quality of life and is used as a measure of benefit in cost-utility analysis. Unfortunately, general PRO instruments such as the EORTC QLQ C30 are not designed to measure subject preferences (or utilities) in a way that is suitable for calculating QALYs. Therefore, a separate validated instrument, in this case the EuroQol EQ 5D, will be used to quantify utilities to calculate QALYs for cost utility analyses.

The EQ 5D is a 5-item questionnaire and a “thermometer” visual analogue scale ranging from 0 (worst imaginable health state) to 100 (best imaginable health state) that will be administered at the same intervals as the other PRO instruments, including at the Screening Visit to assess the comparability of the groups at study initiation. The time referent is “today” for this instrument.

Enhancing Compliance

It is necessary to implement specific measures to ensure optimal compliance in PRO data collection. Both staff and patients will be provided with the necessary training and resources for optimal data collection at the appropriate times. Collaboration between the study coordinator, the data center responsible for the day to day administration of the study and the individual investigators can lead to organizational improvements. More specific measures will be targeted at the patient, the physician and the data manager or the research nurse, though there is considerable overlap.

Missing Data

If a questionnaire is missing during the acceptable time delay, a reason should be recorded (eg, refusal, nurse forgot, etc.), and the patient should be contacted by telephone and mail with the questionnaire and a reply paid envelope. An acceptable time delay or “window” during which the questionnaire must be completed is ± 1 week during treatment, at EOT, and the first two visits post treatment, to ensure evaluation of short-term toxicity and response. During follow up for EQ-5D, a wider window (± 3 weeks) would be acceptable after the first two post-treatment visits.

5.7.2 Healthcare Resource Utilization

During the study, healthcare resource utilization (HRU) data associated with medical encounters related to disease or treatments or both will be collected for all subjects. Specifically, HRU is evaluated based on the number of medical care encounters such as hospital admissions and their duration, outpatient visits, diagnostic tests and procedures, and concomitant medications. HRU data will be collected from all sites. The medical resource utilization data will be utilized to conduct economic analyses.

5.8 Other Assessments

Not applicable.

5.9 Results of Central Assessments

All efficacy laboratory assessments should be performed by the central laboratory. Investigative site staff will receive reports of the results on an ongoing basis for treatment decisions and patient management throughout the study. If the investigator chooses to perform any additional serum and urine myeloma lab tests locally, the results must be reported in the CRF

6 ADVERSE EVENTS

An *Adverse Event (AE)* is defined as any new untoward medical occurrence or worsening of a preexisting medical condition in a clinical investigation subject administered study drug and that does not necessarily have a causal relationship with this treatment. An AE can therefore be any unfavorable and unintended sign (such as an abnormal laboratory finding), symptom, or disease temporally associated with the use of study drug, whether or not considered related to the study drug.

The causal relationship to study drug is determined by a physician and should be used to assess all adverse events (AE). The causal relationship can be one of the following:

Related: There is a reasonable causal relationship between study drug administration and the AE.

Not related: There is not a reasonable causal relationship between study drug administration and the AE.

The term "reasonable causal relationship" means there is evidence to suggest a causal relationship.

Adverse events can be spontaneously reported or elicited during open-ended questioning, examination, or evaluation of a subject. (In order to prevent reporting bias, subjects should not be questioned regarding the specific occurrence of one or more AEs.)

6.1 Serious Adverse Events

A *Serious Adverse Event (SAE)* is any untoward medical occurrence that at any dose:

- results in death
- is life-threatening (defined as an event in which the subject was at risk of death at the time of the event; it does not refer to an event which hypothetically might have caused death if it were more severe)

- requires inpatient hospitalization or causes prolongation of existing hospitalization (see **NOTE** below)
- results in persistent or significant disability/incapacity
- is a congenital anomaly/birth defect
- is an important medical event (defined as a medical event(s) that may not be immediately life-threatening or result in death or hospitalization but, based upon appropriate medical and scientific judgment, may jeopardize the subject or may require intervention [eg, medical, surgical] to prevent one of the other serious outcomes listed in the definition above.) Examples of such events include, but are not limited to, intensive treatment in an emergency room or at home for allergic bronchospasm; blood dyscrasias or convulsions that do not result in hospitalization.) Potential drug induced liver injury (DILI) is also considered an important medical event. (See [Section 6.6](#) for the definition of potential DILI.)

Suspected transmission of an infectious agent (eg, pathogenic or nonpathogenic) via the study drug is an SAE.

Although pregnancy, overdose, cancer, and potential drug induced liver injury (DILI) are not always serious by regulatory definition, these events must be handled as SAEs. (See [Section 6.1.1](#) for reporting pregnancies).

Any component of a study endpoint that is considered related to study therapy (eg, death is an endpoint, if death occurred due to anaphylaxis, anaphylaxis must be reported) should be reported as SAE (see [Section 6.1.1](#) for reporting details).

NOTE:

The following hospitalizations are not considered SAEs in BMS clinical studies:

- a visit to the emergency room or other hospital department < 24 hours, that does not result in admission (unless considered an important medical or life-threatening event)
- elective surgery, planned prior to signing consent
- admissions as per protocol for a planned medical/surgical procedure
- routine health assessment requiring admission for baseline/trending of health status (eg, routine colonoscopy)
- medical/surgical admission other than to remedy ill health and planned prior to entry into the study. Appropriate documentation is required in these cases
- admission encountered for another life circumstance that carries no bearing on health status and requires no medical/surgical intervention (eg, lack of housing, economic inadequacy, caregiver respite, family circumstances, administrative reason).
- Admission for administration of anticancer therapy in the absence of any other SAEs (applies to oncology protocols)

6.1.1 Serious Adverse Event Collection and Reporting

Sections 5.6.1 and 5.6.2 in the Investigator Brochure (IB) represent the Reference Safety Information to determine expectedness of serious adverse events for expedited reporting. Following the subject's written consent to participate in the study, all SAEs, whether related or not related to study drug, must be collected, including those thought to be associated with protocol-specified procedures. All SAEs must be collected that occur during the screening period and within 60 days of discontinuation of dosing or within 30 days of the last visit for screen failures. The investigator must report any SAE that occurs after these time periods and that is believed to be related to study drug or protocol-specified procedure.

An SAE report must be completed for any event where doubt exists regarding its seriousness.

If the investigator believes that an SAE is not related to study drug, but is potentially related to the conditions of the study (such as withdrawal of previous therapy or a complication of a study procedure), the relationship must be specified in the narrative section of the SAE Report Form.

SAEs, whether related or not related to study drug, and pregnancies must be reported to BMS (or designee) within 24 hours of awareness of the event. SAEs must be recorded on the SAE Report Form; pregnancies on a Pregnancy Surveillance Form (electronic or paper forms). The preferred method for SAE data reporting collection is through the eCRF. The paper SAE/pregnancy surveillance forms are only intended as a back-up option when the eCRF system is not functioning. In this case, the paper forms are to be transmitted via email or confirmed facsimile (fax) transmission to:

SAE Email Address: Refer to Contact Information list.

SAE Facsimile Number: Refer to Contact Information list.

For studies capturing SAEs through electronic data capture (EDC), electronic submission is the required method for reporting. In the event the electronic system is unavailable for transmission, paper forms must be used and submitted immediately. When paper forms are used, the original paper forms are to remain on site.

SAE Telephone Contact (required for SAE and pregnancy reporting): Refer to Contact Information list.

If only limited information is initially available, follow-up reports are required. (Note: Follow-up SAE reports must include the same investigator term(s) initially reported.)

If an ongoing SAE changes in its intensity or relationship to study drug or if new information becomes available, the SAE report must be updated and submitted within 24 hours to BMS (or designee) using the same procedure used for transmitting the initial SAE report.

All SAEs must be followed to resolution or stabilization.

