7.6 Safety

Safety summaries will be based on the treated subject population, grouped by treatment regimen received. A subject's treatment regimen received will equal the arm to which the subject was assigned at randomization as long as he did not receive the wrong regimen throughout the study.

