7.6.1 Adverse Events

AEs will be categorized using the most recent version of the MedDRA, by system organ class (SOC) and preferred term. The severity of AEs will be graded using the NCI CTCAE (v 3.0).

On-study AEs are defined as non-serious and serious AEs with an onset date on or after the first dose until 60 days after the last dose. See [Section 8.4](#), Imputing AE Onset Dates, for a discussion of imputation rules for incomplete or missing AE onset dates. If the relationship to study drug is missing, then the AE will be assumed to be related to study drug.

Unless specified otherwise, AEs will be counted only once per subject within each SOC and preferred term, according to their worst CTC grade.

Tables will be sorted by SOC and preferred term, with SOCs ordered by decreasing frequency overall and then alphabetically. Preferred terms will be sorted within SOCs by descending frequency overall and then alphabetically. The sorting will be done based on the total column when arms are presented side-by-side.

The following summaries will be presented by treatment arm:

Frequency tables of the worst grade of on-study AE will be presented: one table with AEs broken out by individual grade (1, 2, 3, 4 or 5) and an Any Grade category and another table in which both arms are included and grades are grouped as follows "Any, Grade 3-4 and Grade 5." The last summary will be repeated for:

- On-study drug-related AEs.
- On-study AEs that occurred \leq Cycle 2 and \geq Cycle 3.

A by-subject listing of all AEs will be presented.

- Exposure-adjusted AE incidence rates (including multiple occurrences of unique events) will be calculated for each SOC and preferred term.

Exposure-adjusted incidence rate per 100 person-years will be used and will be calculated as:

$$100 \times \left(\frac{\text{Total number of unique AEs}}{\frac{\text{subject date of last dose of study drug} - \text{subject date of first dose of study drug} + 60 + 1}{365.25}} \right)$$

and will be displayed along with a count of events

For these additional tables, AEs can be counted multiple times within each SOC and preferred term.

A by-subject listing of unique AEs will be provided.

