7.6.5 Deaths

The number and percentage of deaths and the investigator-reported cause of death will be presented by treatment group. This will be summarized for all deaths, and for those reported on study treatment or within 60 days of discontinuing study treatment.

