7.6.6 Clinical Laboratory Evaluations

On-treatment laboratory tests for safety are defined as those that occur after first dose of any study therapy until 60 days after last dose of any study therapy.

The number and percentage of subjects with each worst severity grade for on-study hematology parameters (hemoglobin, WBC, ANC, ALC and platelets) will be presented, by treatment group. Grades will be categorized as Grade 1, Grade 2, Grade 3, Grade 4, Any Grade and Grade 3-4. Subjects will be counted only once for each parameter, according to their worst post baseline CTC grade. The percentage of subjects with each worst severity grade will be calculated out of the number of treated subjects with on-study assessment for lab parameter. Subjects with a no post-baseline (on-treatment) assessment for a lab parameter will be reported in the “NOT REPORTED” category.

This summary will be repeated for:

- Liver parameters (ALT, AST, alkaline phosphatase, albumin and total bilirubin) with available CTC grades
- Renal/electrolyte parameters (sodium, potassium, bicarbonate, calcium, glucose and creatinine) with available CTC grades

Sodium, potassium, calcium, and random glucose will be presented separately, based on their high and low values.

For blood urea nitrogen (BUN), direct bilirubin and total protein the worst category on-treatment will be presented. Results will be categorized as: below upper normal limits, above upper normal limits or not reported.

For reporting purposes, urea will be converted to BUN, using the conversion factor: $\text{urea (mmol/L)} / 0.357 = \text{BUN (mg/dL)}$.

Subjects experiencing any potential drug induced liver injury (DILI) will be summarized by treatment group and overall as follows:

- A summary of the number and percentage of subjects with (AST or ALT > 3 x upper limit of normal (ULN)) and (Total bilirubin > 2 x ULN and ALP < 2 x ULN) will be presented.

If any potential cases of DILI are identified then clinical review will be conducted to ensure no other immediate apparent possible causes of AT elevation and hyperbilirubinemia are present, including but not limited to, viral hepatitis, pre-existing chronic or acute liver disease, or the administration of other drugs known to be hepatotoxic.

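### The SAP's 60-day safety window has no visible stop at the next anti-myeloma regimen, so next-line events can enter the randomized arm's all-causality and laboratory tables; a cheap sensitivity set would separate them

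*Protocol*

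**What the plan says.** Collection: Protocol 6.1.1 covers SAEs whether related or not: "All SAEs must be collected that occur during the screening period and within 60 days of discontinuation of dosing". Protocol 6.2.1 gives a start for non-serious AE collection but no end.

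Counting: SAP 7.6.1 defines on-study AEs, serious and non-serious, as those "with an onset date on or after the first dose until 60 days after the last dose". SAP 7.6.2 builds the SAE tables on that definition. SAP 7.6.6 defines on-treatment laboratory tests as "those that occur after first dose of any study therapy until 60 days after last dose of any study therapy" and reports each subject's worst grade. SAP 7.6.5 summarizes deaths overall and also those on treatment or "within 60 days of discontinuing study treatment".

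Grouping: "Safety summaries will be based on the treated subject population, grouped by treatment regimen received". That is the randomized arm unless the wrong regimen was given throughout.

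Causality: a separate summary of "On-study drug-related AEs" is planned, and one of related SAEs. The default is: "If the relationship to study drug is missing, then the AE will be assumed to be related to study drug".

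Subsequent therapy: SAP 7.4.6 tabulates and lists it. SAP 8.5 imputes partial start dates, at the earliest to the day after last dose. SAP 4.1.1.4 censors the secondary PFS definition because of it. None of the visible safety sections (7.6 to 7.6.8) uses that date.

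**The concern.** The population is refractory and many subjects will stop at progression, so some will begin another regimen within 60 days of last dose. A cytopenia or infection caused by that regimen falls inside the window and is tabulated under the arm the subject has left. The drug-related tables help, but they rest on open-label investigator attribution and treat missing causality as related. The laboratory tables have no relatedness filter at all. The exposure-adjusted AE rate adds the 60 days to its denominator and keeps the next-line events in its numerator.

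At stake is how cleanly the all-causality and laboratory tables describe the randomized regimens. If one arm stays on drug longer, the dilution is also unequal between arms.

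**Working it through.** **1. Design figure.** SAP 5.1 gives 71 PFS events for HR 0.57, two-sided alpha 0.2, power 85%. Freedman's formula with 1:1 allocation (assumed): (1.2816 + 1.0364)² × (1.57/0.43)² = 5.373 × 13.33 = 71.6, so 72 events. Power at 71 is 0.848. The figure is reproduced. The stated medians imply HR 4.0/6.8 = 0.588 rather than 0.57; the medians are used below.

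**2. Inputs.** Medians of 4.0 (Pd) and 6.8 (E-Pd) months, exponential; accrual over 9 months; PFS analysis at 9 + 6 = 15 months; OS analysis 18 months later, at 33 (SAP 5.1, 5.3). Window W = 60/30.4375 = 1.97 months. Assumptions not in the documents: time on drug equals PFS time, no deaths within the window, every subject who stops switches, and the switch comes 14-28 days after last dose.

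**3. Share of counted time after last dose, unlimited follow-up.** W/(median/ln 2 + W):
- Pd: 1.97/(5.77 + 1.97) = 25.5%
- E-Pd: 1.97/(9.81 + 1.97) = 16.7%

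**4. At the 15-month cut-off** (simulation, 1,000,000 subjects per arm):

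| Per subject | Pd | E-Pd |
|---|---|---|
| Months on drug | 4.74 | 6.33 |
| Months in post-dose window | 1.55 | 1.20 |
| Window share of counted time | 24.7% | 15.9% |
| Next-line share, switch at day 14 | 18.7% | 12.0% |
| Next-line share, switch at day 28 | 12.9% | 8.2% |

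At 33 months, window time is 1.95 vs 1.85 months per subject. The per-subject asymmetry has almost gone, although the window share still differs (25.4% vs 16.7%).

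**5. Crude SAE percentage**, assuming the same hazard of 0.08/month on any therapy in both arms (accrual at 13/month, 400,000 subjects per arm):
- Pd: 37.9% as planned; 31.2% (day 14) to 33.4% (day 28) truncated. Rise of 6.7 to 4.5 points.
- E-Pd: 43.5% as planned; 38.5% to 40.2% truncated. Rise of 5.0 to 3.3 points.
- Between-arm shift: 6.7 − 5.0 = 1.7, or 4.5 − 3.3 = 1.2 points. With 57 per arm that is 0.7 to 1.0 subject. The standard error of the difference is √[(0.379×0.621 + 0.435×0.565)/57] = 9.2 points.
- Crude gap, E-Pd minus Pd: 43.5 − 37.9 = 5.6 as planned; 38.5 − 31.2 = 7.3 or 40.2 − 33.4 = 6.8 truncated. There is no true excess in this scenario; the gap comes from longer time on drug, and truncation alone widens it.

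**6. Exposure-adjusted rate**, using observed person-time and a day-14 switch:
- Equal hazards: 0.08 × 12 × 100 = 96 per 100 person-years in both arms, truncated or not.
- Assumed true excess, 0.10 vs 0.08/month. E-Pd time is 6.62 months before the switch and 0.90 after; Pd time is 5.11 and 1.18.
  - Next-line hazard 0.08: E-Pd (0.662 + 0.072)/7.53 = 0.0976; ratio to 0.08 is 1.22 instead of 1.25.
  - Next-line hazard 0.15: E-Pd (0.662 + 0.135)/7.53 = 0.106; Pd (0.409 + 0.176)/6.29 = 0.093; ratio 1.14.
- Truncating numerator and denominator restores 1.25.

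The formula printed in SAP 7.6.1 adds the full 60 days for everyone, including subjects still on drug at cut-off, so its denominator needs an explicit end date in any truncated version.

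**The case against.** A reader might infer that next-line toxicity will be reported as toxicity of the randomized arm, more so in Pd, and that this hides an excess with elotuzumab. The documents do not support that.

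- **Attribution.** All-causality tables do not attribute. Drug-related AE and SAE tables, investigator-reported cause of death, and AE and subsequent-therapy listings are planned. Protocol 6.1 excludes admissions made only to give anticancer therapy from SAEs. This stands, though the separation is partial.
- **Direction.** Nothing in the documents describes a difference between arms in this window. It follows only if E-Pd prolongs time on drug; with equal time on drug there would be none. In the equal-hazard example, truncated crude percentages move further from the truth. This stands, and it shapes the fix.
- **Size.** The switch rate and gap are not given, and assuming that all stoppers switch is an upper bound. If 60% switched (assumption), the between-arm shift would be 0.6 × 1.2 to 0.6 × 1.7, about 0.7-1.0 points. This stands.
- **Laboratory values.** It is tempting to say that a next-line cytopenia becomes the worst grade. That needs the value to be collected and to exceed the earlier worst. Protocol 5.3 restricts submission to protocol-specified data, and the post-treatment schedule (Table 5.1-3) is not shown in the public text. Such values can enter; how many do is unknown.
- **Silence.** SAP 8.6 defers to an outside safety convention, and parts of the SAP are redacted. A stop rule may exist there. However, 7.6.1 and 7.6.6 state explicit windows without one, so any such rule should be named in them.

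**Conclusion.** The gap is real but modest. The visible SAP counts AEs, SAEs and worst laboratory grades to 60 days after last dose with no stop at subsequent systemic therapy, although it handles that date elsewhere. Next-line events can therefore enter the randomized arm's all-causality and laboratory tables.

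At the 15-month PFS cut-off, which SAP 7.5 makes the basis of the study report, next-line time is at most 13-19% (Pd) and 8-12% (E-Pd) of counted time, if all stoppers switch at 14-28 days. The between-arm effect is about 1-2 points in crude SAE percentage, roughly one subject per arm and well inside sampling error. It depends on E-Pd prolonging time on drug and nearly disappears per subject at the OS cut-off. A true rate ratio of 1.25 would be diluted to about 1.22, or 1.14 if the next regimen were considerably more toxic. All hazards and switch times are assumptions. This is a low-priority, cheap improvement and does not threaten the trial's conclusions.

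**What to change.** Leave collection and the planned tables as they are. In SAP 7.6.1, 7.6.2 and 7.6.6 add:

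1. Sensitivity versions of the AE, SAE, Grade 3-5 and worst-laboratory-grade tables, with the window ending at the earlier of last dose + 60 days and the day before the first subsequent systemic anti-myeloma therapy.
2. The exposure-adjusted AE rate with numerator and denominator both ended at that date.
3. The number of events by arm with onset on or after the start of that therapy and still within 60 days of last dose.

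State that arms are compared on the truncated exposure-adjusted rate, because truncated crude percentages still reflect unequal time on drug. If the convention cited in SAP 8.6 already contains a stop rule, say so in 7.6.1 and 7.6.6.

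Cost: some SAP wording and a few repeated tables from dates already collected. Downside: delayed effects of study drug that appear after a switch show only in the original tables, which is why those must stay.
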